4.8.2.	Adverse Events	.23
4.8.3.	Patient Narratives	.23
4.8.4.	Vital Signs	.24
4.8.5.	Electrocardiograms	.24
4.8.6.	Clinical Laboratory Evaluation	.25
4.8.7.	Additional Safety Assessments	.25
4.9.	Subgroup Analyses	.28
4.10.	Interim Analyses	.29
4.11.	Changes to Protocol-Planned Analyses	.29
5.	Sample Size Determination	.30
6.	Supporting Documentation	.31
6.1.	Appendix 1: Demographic and Baseline Characteristics	.31
6.2.	Appendix 2: Historical Illnesses and Pre-existing Conditions	.31
6.3.	Appendix 3: Treatment Compliance	.31
6.4.	Appendix 4: Concomitant Medications	.31
6.5.	Appendix 5: Important Protocol Deviations	.31
6.6.	Appendix 6: Searching Criteria for Additional Safety	
	Assessments	.32
7.	References	.33

CONFIDENTIAL

Version history

This statistical analysis plan (SAP) for Study J3L-MC-EZEB (EZEB) is based on the protocol dated 19 July 2022.

SAP Version	Approval Date	Change	Rationale
1	04 Apr 2023	Not Applicable	Original version
2	30 June 2023	 Added acronym for the study in front page. Clarified the definition of full analysis set (FAS) in Section 3. Updated analysis method for time-averaged endpoint in Section 4.3.2. Changed language in Section 4.1 and Section 4.4.2 to reflect updates. Updated analysis for hypersensitivity events in Section 4.8.7.2. Updated the renal safety analysis in Section 4.8.7.4. Removed Appendix 7. Adjusted formatting of Table 4.7. Removed KM plot in Section 4.2. Adjusted subgroup analyses in Section 4.9. 	 Added acronym for the study in front page. Clarified the definition of FAS in Section 3. Instead of original approach using multiple imputation, MMRM approach is applied to analyze time-averaged endpoint. Updated analysis for hypersensitivity events in Section 4.8.7.2 per Phase 1 results. Updated the unit for UACR. The slope analysis is not required for the non-CKD population. Safety analyses defined in Appendix 7 are not needed for Phase 2 studies. KM plots for patients' disposition are not required for this study because there are only 2 injections in total. Redefined the subgroup analyses because the number of participants is too small (less than 10%) within a subgroup.

Table 1. SAP Version History Summary

SAP Version	Approval Date	Change	Rationale
		• Added more time averaged endpoints for the first secondary objective in Section 1.1	 Percent change from baseline on time averaged Lp(a) over Days 30-180, and Days 30-360 were put in incorrect cell.
3	See data on Page 1	 Modified the error for time averaged Lp(a) analysis in Table 4.2 and Table 4.5. Removed "ANCOVA" from footnote. Updated the searching criteria for TEAE hypersensitivity events in Section 6.6 Appendix 6. Reworded the model in Section 4.3.2 Removed the publication not cited in the document from "References" 	 Revised the text in the table and made it consistent with the SAP body. The original searching criteria are not accurate. Updated per team discussion. The expression was updated with re-defining betas as least-squares means which make the wording less confusing. Two publications in "References" were not cited in the text.

Abbreviations: ANCOVA = analysis of covariance; CKD = chronic kidney disease; KM = Kaplan-Meier;

Lp(a) = lipoprotein(a); MMRM = mixed model repeated measures; SAP = statistical analysis plan;

TEAE = treatment-emergent adverse event; UACR = urine albumin-to-creatinine ratio.

1. Introduction

1.1. Objectives, Endpoints, and Estimands

Endpoints	
 Percent change from baseline in time- averaged Lp(a) over Days 60-180 	
 Percent change from baseline in time-averaged Lp(a) over Days 240-360, Days 30-180, and Days 30-360 Proportion of participants achieving Lp(a) <125 and <75 nmol/L at Days 60, 180, 240, 360, and 540 Percent change from baseline and absolute change from baseline to Days 60, 180, 240, 360, and 540 for Lp(a) ApoB bsCRP 	
Population PK parameters	
· · · ·	
 Absolute change from baseline in Lp(a) at Days 60, 180, 240, 360, and 540 Proportion of participants achieving Lp(a) lowering of at least 150 nmol/L at Days 60, 180, 240, 360, and 540 	
 Percent change from baseline and absolute change from baseline for lipid profile LDL-C total cholesterol HDL-C triglycerides Incidence of treatment-emergent ADAs 	

Abbreviations: ADA = antidrug antibody; ApoB = apolipoprotein B; HDL-C = high-density lipoprotein-cholesterol; hsCRP = high-sensitivity C-reactive protein; LDL-C = low-density lipoprotein-cholesterol;

Lp(a) = lipoprotein(a); PK = pharmacokinetics.

Primary estimand

The primary clinical question of interest is: What is the intervention difference in percent change from baseline in time-averaged lipoprotein(a) (Lp[a]) over Days 60 to 180 of study intervention in participants who meet the inclusion criteria regardless of treatment discontinuation or initiation of excluded medications and Lp(a) modifying medication for any reason?

The primary estimand characterizes the treatment effect regardless of intercurrent events (ICEs) and is named the "treatment-regimen estimand."

CONFIDENTIAL

The treatment-regimen estimand is described by the following attributes:

- Population: participants who meet the enrollment criteria. Further details can be found in Section 5 and Section 9 of the study protocol EZEB.
- Endpoint: percent change from baseline in time-averaged Lp(a) over Days 60 to 180, which will be calculated by area under the curve (AUC) between Day 60 to Day 180 divided by 120.
- Treatment condition: the randomized treatment. Further details on study interventions, and concomitant interventions can be found in Section 6 of the study protocol EZEB.

There are no ICEs, because treatment discontinuation and initiation of medications that are known to impact Lp(a) level are part of the treatment condition.

Population-level summary: percent change from baseline in time-averaged Lp(a) over Days 60 to 180.

Treatment contrast of interest: difference in percent change from baseline in time-averaged Lp(a) over Days 60 to 180 between each dose of LY3819469 and placebo.

Rationale for estimand: this estimand aims to study the efficacy of LY3819469 that reflects the real-life behavior of the target population.

Safety

Unless specified otherwise, safety assessments will be guided by an estimand comparing safety of LY3819469 doses with placebo irrespective of adherence to study intervention.

Efficacy estimand

The efficacy estimand answers the question: What is the treatment difference in percent change from baseline in time-averaged Lp(a) over Days 60 to 180 after a single dose of LY in participants who meet the inclusion criteria and would have completed the treatment period without initiation of medications that are known to impact Lp(a) levels?

The "efficacy estimand" is described by the following attributes:

- Population: participants who meet the enrollment criteria. Further details can be found in Section 5 and Section 9 of the Study Protocol J3L-MC-EZEB.
- Endpoint: percent change from baseline in time-averaged Lp(a) over Days 60 to 180, which will be calculated by AUC between Day 60 to Day 180 divided by 120, and
- Treatment condition: the randomized treatment.

The ICEs "permanent discontinuation of intervention" and "initiation of excluded medications taken during the study or new initiation of any Lp(a) modifying medication per the protocol inclusion criteria" are handled by the hypothetical strategy where the potential outcome of interest is the response in the efficacy measurement if participants had adhered to the randomized treatment without using such medication. Analyses post–Day 180 will also consider the ICE of "treatment discontinuation". There are no other defined ICEs. Switching medications within a class (for example, from one statin to another) is not considered an ICE for the definition of estimand in this study.

Population-level summary: percent change from baseline in time-averaged Lp(a) over Days 60 to 180.

Treatment contrast of interest: difference in percent change from baseline in time-averaged Lp(a) over Days 60 to 180 between each dose of LY3819469 and placebo.

Rationale for estimand: this estimand aims to study the efficacy of LY3819469 under the ideal condition that all participants adhere to their randomly assigned treatment without being confounded by the initiation of other medication that are known to impact Lp(a) levels.

1.2. Study Design

Study J3L-MC-EZEB is a parallel, double-blinded, placebo-controlled, dose-finding, Phase 2 study of LY3819469 in participants with elevated Lp(a). The purpose of this study is to measure difference in percent change from baseline in time-averaged Lp(a) over Days 60 to 180 with LY3819469 versus placebo in participants with elevated Lp(a). The duration of the study will be up to 20 months. The study will consist of an optional prescreening period, an approximately 21-day screening period followed by a 540-day treatment and assessment period.

Participants will be randomly assigned in a 1:2:2:2:2 ratio to one of the following arms:

- Arm A: 16-mg LY3819469, dosed at randomization and Day 180
- Arm B: 96-mg LY3819469, dosed at randomization and Day 180
- Arm C: 400-mg LY3819469, dosed at randomization and Day 180
- Arm D: 400-mg LY3819469, dosed at randomization, placebo at Day 180, and
- Arm E: placebo, dosed at randomization and Day 180.

This is a double-blind study in which participants are blinded to study intervention. Placebo participants will be randomly assigned so that each dose cohort will have a matching placebo cohort that receives the same dose volume to maintain the study blind. The matching placebo-treated patients will be pooled for all statistical analysis.

Participants will be stratified by high risk for cardiovascular events (yes/no) and baseline Lp(a) (<275 nmol/L, \geq 275 nmol/L). High risk for cardiovascular events will be defined as coronary artery disease (including coronary artery disease, coronary artery bypass graft, myocardial infarction, percutaneous coronary intervention, and unstable angina), stroke (cerebrovascular accident), or peripheral artery disease, or atherosclerotic cardiovascular disease (ASCVD) risk equivalents (familial hypercholesterolemia or type 2 diabetes).

Figure 1.1 Illustration of study design for clinical protocol J3L-MC-EZEB.

2. Statistical Hypotheses

The null hypothesis to be tested in relation to the primary estimand is as follows:

• LY3819469 16 mg, 96 mg, or 400 mg is not different from placebo with respect to percent change in Lp(a) from baseline in time-averaged Lp(a) over Days 60 to 180.

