A similar estimand as the estimand for the primary objective will be used for the secondary objectives.

Unless specified otherwise, safety assessments will be guided by an estimand comparing safety of LY3819469 doses with placebo irrespective of adherence to study intervention.

Overall Design

Study is a parallel, double-blinded, placebo-controlled, dose-finding, Phase 2 study of LY3819469 in participants with elevated Lp(a).

Approximately 254 participants will be randomized in a 1:2:2:2:2 ratio to 1 of the following arms:

- Arm A: 16-mg LY3819469, doses at randomization and Day 180
- Arm B: 96-mg LY3819469, doses at randomization and Day 180
- Arm C: 400-mg LY3819469, doses at randomization and Day 180
- Arm D: 400-mg LY3819469, dosed at randomization, placebo at Day 180
- Arm E: placebo, doses at randomization and Day 180

Brief Summary:

The purpose of this study is to measure difference in percent change from baseline in timeaveraged Lp(a) on over Days 60-180 with LY3819469 versus placebo in participants with elevated Lp(a).

Study details include:

- The study duration will be up to 20 months.
- The treatment duration will include doses at the randomization visit and at Day 180.

Study Population:

The study will include adults at least 40 years old. People in the study who are on particular medicines should stay on the same doses for the whole study. People who have had a major illness or surgery in the 3 months prior to the study will not participate. People who have certain abnormal laboratory values will not be included.

Number of Participants:

Approximately 254 participants will be randomly assigned to study intervention.

Intervention Groups and Duration:

All participants will receive a subcutaneous injection at the randomization visit and at Day 180 (Visit 7). LY3819469 is formulated at a concentration of 160 mg/mL.

	Arm A	Arm B	Arm C	Arm D	Arm E
Intervention Name	LY3819469	LY3819469	LY3819469	LY3819469 and Placebo	Placebo ^a
Dosage #1					
LY3819469 Solution (160mg/mL)	16 mg (0.1 mL)	96 mg (0.6 mL)	400 mg (2.5 mL)	400 mg (2.5 mL)	_
Placebo (0.9% sodium chloride solution for injection)	_	_	_	_	Placebo ^a
Dosage #2					
LY3819469 Solution (160mg/mL)	16 mg (0.1 mL)	96 mg (0.6 mL)	400 mg (2.5 mL)	_	_
Placebo (0.9% sodium chloride solution for injection)	_	_	_	Placebo ^b	Placebo ^a
Route of Administration	SC injection	SC injection	SC injection	SC injection	SC injection

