## 6.1. Study Intervention(s) Administered

Abbreviations: EU = European Union; SC = subcutaneous.

- ^a Participants in Arm E will be randomly assigned so that each dose cohort will have a matching placebo cohort that receives the same dose volume to maintain the study blind.
- ^b Participants in Arm D will receive a 2.5-ml placebo dose at Day 180 (Visit 7).

The table below describes the injection volume for the different intervention dose groups.

Intervention Group	Injection volume
16 mg or matched placebo participants	0.1 mL
96 mg or matched placebo participants	0.6 mL
400 mg or matched placebo participants	2.5 mL

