## 6.3. Measures to Minimize Bias: Randomization and Blinding

All participants will be centrally assigned to randomized study intervention using an Interactive Web-Response System (IWRS). Participants will be stratified by high risk for cardiovascular events (yes/no) and baseline Lp(a) (<275 nmol/L,  $\geq$ 275 nmol/L). Placebo participants will be randomly assigned so that each dose cohort will have a matching placebo cohort that receives the same dose volume to maintain the study blind. Before the study is initiated, the log in information and directions for the IWRS will be provided to each site.

Study intervention will be dispensed and administered at the study visits summarized in SoA.

This is a double-blind study in which participants are blinded to study intervention. The IWRS will be programmed with blind-breaking instructions. In case of an emergency, the investigator has the sole responsibility for determining if unblinding of a participants' intervention assignment is warranted. Participant safety must always be the first consideration in making such a determination. If the investigator decides that unblinding is warranted, the investigator should make every effort to contact the sponsor prior to unblinding a participant's intervention assignment unless this could delay emergency treatment for the participant. If a participant's intervention assignment is unblinded, the sponsor must be notified immediately within 24 hours of this occurrence. The date and reason that the blind was broken must be recorded.

If an investigator, site personnel performing assessments, or participant is unblinded, the participant may be continued in the study.

Investigators will remain blinded to each participant's assigned study intervention throughout the course of the study. To maintain this blind, an otherwise uninvolved third party will be responsible for the preparation and dispensation of all study intervention and will endeavor to ensure that there are no differences in time taken to dispense following randomization.

This third party will instruct the participant to avoid discussing the volume of injection, dosing frequency, or packaging of the study intervention with the investigator.

In the event of a quality assurance audit, the auditor(s) will be allowed access to unblinded study intervention records at the site(s) to verify that randomization/dispensing has been done accurately.

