4.8.7.3. Injection Site Reactions

Injection site reactions, incidence, and related information reported in eCRFs will be summarized by treatment. Information to be summarized includes the timing of the reaction relative to study drug administration, and characteristics of the injection site reaction: erythema, induration, pain, pruritus, and edema.

Additionally, potential injection site reactions will be searched by predefined MedDRA high level terms (HLTs) of injection site reactions, administration site reactions, and infusion-related reactions. Detailed searching criteria for injection site reaction events can be found in Appendix 6 (Section 6.6). The PT will be used for summary by treatment within each HLT category.

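### Pooling placebo injections of 0.1, 0.6 and 2.5 mL for every analysis lets any injection-volume effect enter the injection-site reaction comparisons, although volume-matched placebo cohorts are available

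*SAP*

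**What the plan says.** Protocol 1.1 fixes the strength: "LY3819469 is formulated at a concentration of 160 mg/mL". Volume therefore rises with dose. The table in Protocol 6.1 gives 0.1 mL for "16 mg or matched placebo participants", 0.6 mL for "96 mg or matched placebo participants" and 2.5 mL for "400 mg or matched placebo participants".

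Arm E is divided by randomisation so that "each dose cohort will have a matching placebo cohort that receives the same dose volume to maintain the study blind"; Protocol 6.3 repeats this. A footnote in Protocol 6.1 adds that Arm D, which receives 400 mg at randomisation, receives 2.5 mL of placebo at Day 180.

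SAP 1.2 then states the analysis rule: "The matching placebo-treated patients will be pooled for all statistical analysis". It makes no exception for any outcome. On local tolerability, SAP 4.8.7.3 says: "Injection site reactions, incidence, and related information reported in eCRFs will be summarized by treatment". The MedDRA term search in the same section is also presented by treatment. Timing relative to dosing is to be summarised, but nothing is split or adjusted by volume, and Appendix 6 adds only search terms.

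Formal testing comes from the general rules. Protocol 9.3.5 compares adverse events between groups by Fisher's exact test, and SAP 4.8.2 applies comparisons at the system organ class and preferred term levels. SAP 4.1 limits comparisons to active against placebo unless otherwise specified. SAP 4.8 allows the two 400-mg arms to be pooled for safety.

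**The concern.** For Lp(a), the volume of saline injected should not matter, and pooling placebo gains precision. Local reactions are different, because volume may itself influence them. An active-minus-pooled-placebo difference then holds two components: the effect of the drug and the effect of injecting a different volume from the average placebo participant.

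The active arms cannot separate these components, because at a single concentration dose and volume move together. The randomised volume-matched placebo cohorts can, but the pooling rule removes them from view for the one group of outcomes where they are most informative.

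The study is meant to inform dose selection for Phase 3. Protocol 4.3 says the dose range supports dose-exposure-response analysis of safety as well as efficacy, and Protocol 9.5 says the sample size was judged appropriate for providing safety data. A volume artefact read as local intolerance to the drug would count against 400 mg and flatter 16 mg.

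**Working it through.** **The plan's own figures.** With N = 254 and allocation 1:2:2:2:2, the 16-mg arm has 254 × 1/9 = 28.2 participants and every other arm, including placebo, has 254 × 2/9 = 56.4. After 15% dropout these become 28.2 × 0.85 = 24.0 and 56.4 × 0.85 = 48.0, which match the stated 24 and 48 completers. The documents state no figure for injection-site reactions or for the size of any placebo volume cohort.

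**Volumes.** 16/160 = 0.1 mL, 96/160 = 0.6 mL and 400/160 = 2.5 mL. The range is 2.5/0.1 = 25-fold.

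**Form of the bias.** For an active group with volume v:

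(active − pooled placebo) = (active − placebo at v) + (placebo at v − pooled placebo)

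The last bracket is the bias relative to the volume-matched difference. It does not depend on the size of the drug effect, and it is zero if placebo risk is the same at all volumes.

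**Assumed inputs.** Two are needed and neither is in the documents:
- Saline reaction rates at 0.1/0.6/2.5 mL: 2/5/12% or 1/3/6%.
- Division of about 56 placebo participants: 1:2:4 (8, 16 and 32, proportional to the active participants at each volume) or 1:1:1 (about 19 each).

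**Pooled placebo rates.**
- 2/5/12%, 1:2:4: (8 × 2 + 16 × 5 + 32 × 12)/56 = 480/56 = 8.57%
- 2/5/12%, 1:1:1: (2 + 5 + 12)/3 = 6.33%
- 1/3/6%, 1:2:4: (8 × 1 + 16 × 3 + 32 × 6)/56 = 248/56 = 4.43%

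**Bias in percentage points (matched rate minus pooled rate).**

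| Assumed rates | Division | 16 mg | 96 mg | 400 mg |
|---|---|---|---|---|
| 2/5/12% | 1:2:4 | -6.6 | -3.6 | +3.4 |
| 2/5/12% | 1:1:1 | -4.3 | -1.3 | +5.7 |
| 1/3/6% | 1:2:4 | -3.4 | -1.4 | +1.6 |
| equal at all volumes | any | 0 | 0 | 0 |

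**Effect on a test, for illustration.** Suppose the drug causes no reactions, saline rates are 2/5/15%, and 112 participants on 400 mg (both arms) are compared with 56 pooled placebo participants by a two-sided Fisher's exact test at 0.05. The exact chance of a significant but spurious 400-mg excess is 8.6% (1:2:4) or 23.0% (1:1:1). Against 2.5-mL placebo alone it is 1.7% or 0.9%. With a 5% rate at every volume, the chance against pooled placebo is 0.7%.

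**Precision of the matched cells.** With 8 placebo participants at 0.1 mL and no reactions, the exact two-sided 95% upper limit is 1 − 0.025^(1/8) = 36.9%.

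**The case against.** The strongest counter-argument is that the size of the problem is wholly assumed. No section gives a reaction rate, a volume effect or the division of Arm E. Protocol 2.2.4 and 2.3.1 describe single doses up to 608 mg as generally well tolerated with no notable adverse drug effects, although neither addresses local reactions specifically. This stands: the direction is conditional on risk rising with volume, and the figures are scenarios.

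The matched cohorts also exist to protect the blind, and the documents say nothing more about their purpose. A reader might infer that pooling contradicts a declared intention to use them as separate comparators. The documents do not support that. Their value as concurrent randomised controls at the same volume is a reason to use them, not a commitment that was broken.

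A reader might also infer that the plan will test a dose-response in local tolerability that is really a volume response. It will not: SAP 4.1 excludes comparisons across doses unless otherwise specified, and SAP 4.8.7.3 only summarises. Any such reading would be a descriptive one from a side-by-side table. Tests against placebo remain possible through the general adverse event rules.

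Pooling has a real precision argument, since about 8 participants cannot support a useful 0.1-mL contrast. That limits what the matched table can show, but it does not make the pooled comparison answer the drug question. The general allowance in SAP 4.1 for additional analyses is not a commitment to this one, and a display chosen after unblinding carries less weight than one set out beforehand.

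**Conclusion.** The point holds as a minor one, confined to local-tolerability outcomes. Applied as written, the pooling rule compares each single-volume active group with a mixture of three placebo volumes. If reaction risk rises with volume, the excess is overstated for 400 mg and understated for 16 mg. In the scenarios with a volume effect, the bias runs from +1.6 to +5.7 points for 400 mg and from -3.4 to -6.6 points for 16 mg; without a volume effect it is zero.

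Two stronger readings are not supported. The documents do not show that the reported results will be biased, because they contain no evidence on a volume effect. Nor does this touch the primary or secondary efficacy endpoints, for which nothing suggests that placebo volume matters.

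**What to change.** - Keep the pooled placebo for efficacy and systemic safety. In SAP 1.2, except injection-site reactions from the pooling sentence.
- In SAP 4.8.7.3, add a table by injection volume and injection number (first dose, Day 180 dose), active against volume-matched placebo, with a risk difference and confidence interval for each volume.
- Give a volume-stratified overall difference only as a supplement. It averages over three doses, so it does not answer the question for any one of them.
- Classify Arm D's Day 180 injection as 2.5 mL of placebo given after earlier active dosing. Show it on its own line and do not count it as an active injection. Without this, pooling the two 400-mg arms would credit reactions to saline to the drug.
- State the division of Arm E across volumes, and label the 0.1-mL row and any reading across doses as descriptive.

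The cost is one extra safety table and a short SAP edit. Design, conduct and the primary analysis do not change. The drawback is small matched placebo cells: about 8, 16 and 32 under a 1:2:4 division, or about 19 each under 1:1:1.
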